## LIST OF ABBREVIATIONS

78		
79		
80	AA	African American
81	ACQ	Asthma Control Questionnaire
82	ACTION	physicAl aCtiviTy In minOrity womeN with asthma
83	DSMP	Data and Safety Monitoring Plan
84	EHR	Electronic Health Record
85	HIPAA	Health Insurance Portability and Accountability Act
86	IRB	Institutional Review Board
87	ISWT	Incremental Shuttle Walk Test
88	NIH	National Institutes of Health
89	OPRS	Office for the Protection of Research Subjects
90	PA	Physical Activity
91	PHI	Protected Health Information
92	PI	Principal Investigator
93	SAE	Serious Adverse Event
94		
95		

96 **1.0 Project Summary/Abstract**

97 Physical inactivity in asthma is associated with worse asthma outcomes and African  
98 American women are disproportionately impacted by both physical inactivity and  
99 asthma. Research aimed at addressing the unique asthma-related and cultural-specific  
100 barriers to physical activity in this vulnerable population of women is needed. The  
101 proposed study will modify a validated community-based walking intervention specific to  
102 the needs of sedentary African American women with asthma and evaluate the impact  
103 of the intervention on physical activity and asthma specific indicators to reduce the  
104 burden of asthma in sedentary African American women.  
105

## 106 2.0 Background/Scientific Rationale

107 Asthma is a highly prevalent chronic disease that disproportionately impacts African  
108 American (AA) women. AA women have poorer asthma-related quality of life and higher  
109 rates of asthma exacerbations, healthcare utilization and mortality compared to  
110 Caucasian women. Further, AA women are less physically active than any other  
111 subgroup of adults, which may help explain the asthma health disparities, found  
112 between AA and Caucasian women. Physical inactivity among individuals with asthma  
113 is associated with poor asthma control and respiratory function, greater health care  
114 utilization, and poorer quality of life. Given the connection between poor asthma  
115 outcomes and physical inactivity, addressing physical activity (PA) among sedentary AA  
116 women with asthma is imperative. Physical activity demonstrated improvement in  
117 asthma outcomes specifically asthma control, quality of life and healthcare utilization.  
118 Despite these benefits, fewer than 25% of AA women with asthma engage in regular  
119 physical activity. The **ACTION intervention: physicAl aCtivity In minOrity womeN  
120 with asthma** is a 8-month community-based walking intervention refined to be  
121 applicable for sedentary AA women with asthma.  
122

123 This project will obtain and incorporate stakeholder input on the barriers and facilitators  
124 to engaging in physical activity with asthma to a validated community-based walking  
125 intervention. Once modified, we will pre-pilot the intervention in 10 participants, refine  
126 further in response to participant feedback and then test the feasibility, acceptability and  
127 estimate the efficacy of the intervention in a randomized controlled pilot of 80  
128 participants within a pragmatic community setting convenient for sedentary AA women.  
129

## 131 3.0 Objectives/Aims

132 The proposed study has 5 aims involving a total of 135 sedentary AA women with  
133 asthma.  
134

135 **NOTE:** Aims 1 and 2 have been IRB approved and completed. Only data analysis of  
136 these 2 aims are still occurring. At this time, I am requesting approval for Aim 3 which  
137 entails pilot testing the intervention to assess the feasibility, acceptability and to  
138 estimate the efficacy of the ACTION intervention.  
139

140 **Aim 1:** Use stakeholder input to modify a validated walking intervention for sedentary  
141 AA women with asthma.

[figure not shown]
142 **Aim 1a:** Conduct focus groups in 30 sedentary AA women with asthma to assess PA  
143 barriers and facilitators.  
144

145 **Aim 1b:** Adapt a validated walking intervention that addresses the barriers and  
146 facilitators to PA unique to sedentary AA women with asthma obtained from Aim 1A.  
147  
148

149 **Aim 2:** Pre-pilot test ACTION (physicAl aCtivity In minOrity womeN with asthma)  
150 intervention in up to 10 sedentary AA women with asthma to refine the recruitment  
151

152 materials, approach, design, and intervention content.

[figure not shown]
Figure 1. Study Design for ACTION Pre-pilot

153  
154  
155  
157  
158  
159  
160

**Aim 3:** Pilot test ACTION intervention in 80 sedentary AA women with asthma to assess acceptability, feasibility and estimate the efficacy to appropriately power a subsequent efficacy trial.

Figure 2. Study Design for Aim 3 (ACTION RCT Pilot)

161  
162  
163  
164  
165  
166  
167  
168  
169  
170  
171  
172  
173  
174  
175  
176

**Aim 4:** Modify and refine the video component of the intervention to address the asthma-specific barriers to walking in AA women with asthma.

**Aim 4a:** Conduct a focus group with an Asthma Advisory Council (AAC) that includes up to 15 AA women with asthma, to assess the appropriateness of the proposed asthma content, language and setting used in the videos.

**Aim 4b:** Adapt the video component of the intervention using an iterative approach to include appropriate asthma content, language and setting.

**Aim 5:** Assess the acceptability of the revised videos by the AAC using a mixed methods approach (qualitative and quantitative data).

**Aim 6:** Disseminate research findings and next steps to women that participated in Aims 1-3.

177 **4.0 Eligibility/Inclusion and Exclusion Criteria (for Aims 1, 2 and 3)**

178

179 Participants will be recruited from the UI Health System.

180

- 181 • **Eligibility considerations:** We chose to focus on sedentary AA women with
- 182 sub-optimally controlled persistent asthma (based on ACQ score  $\geq 1.5$ /Appendix
- 183 1 OR ACT score  $\geq 20$ /Appendix 2) as long-term goal is to see an effect change in
- 184 asthma control. During our focus groups, we will discuss if there is a preferred
- 185 age range and will refine the intervention accordingly. Focus group participants
- 186 did not express a preferred age range so a diverse age range of participants will
- 187 be recruited to ensure representation from a diverse population of AA women
- 188 with asthma. Women that have completed participation in Aims 1, 2, or 3 of this
- 189 study will be able to participate in Aims 4 and 5 of the study.

190

191

192 **4.1 Inclusion Criteria**

193 **4.1.a. Aims 1 and 2:**

194

195

196

197

198

199

200

- Self-identify as female and black or AA
- Age 18-70
- Self-report  $< 150$  min/week of moderate intensity PA
- Sub-optimally controlled persistent asthma based on Asthma Control Questionnaire (ACQ  $\geq 1.5$ ) OR Asthma Control Test (ACT  $< 20$ )
- Willing to enroll and provide written-informed consent

201 **4.1.b. Aim 3**

202

203

204

205

206

207

208

209

- Self-identify as female and black or AA
- Age 18-70
- Sub-optimally controlled persistent asthma based on Asthma Control Test (ACT  $< 20$ )
- Willing to enroll and provide written-informed consent
- Have a smartphone or tablet device
- Willing to be randomly assigned to treatment or control group

210 **4.1.c. Aims 4 and 5**

211

212

213

214

215

216 **4.2 Exclusion Criteria:**

217

217 **4.2.a. Aims 1 and 2**

218

219

220

221

- Plans to move from Chicago during the study period
- Unable to ambulate without human assistance
- History of significant mental illness (e.g. uncontrolled bipolar disorder, psychoses)

- 222 • Currently pregnant, planning to become pregnant over the next 3 months
- 223 • Diagnosis of COPD (emphysema or chronic bronchitis) suggested by patient
- 224 report of doctor diagnosis or smoking history (>20 pack years)
- 225 • Family/household member of another study participant or staff member
- 226 • Inability to speak, read or understand English;
- 227 • Investigator discretion for safety or protocol adherence reasons

228  
229

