### 274 **4.3 Excluded or Vulnerable Populations**

275 **EXCLUSION OF MINORS** Although asthma is a disease that affects both children and  
276 adults the focus of this proposal is to specifically modify and pilot test an existing  
277 physical activity intervention in sedentary African American women with asthma.  
278 Children are intentionally being excluded, as currently there is insufficient data available  
279 in African American adults with asthma to judge the potential risk of this intervention in  
280 children.  
281

282 **INCLUSION OF WOMEN AND MINORITIES** The focus population for this study is  
283 sedentary African-American (AA) women with asthma. All participants included in the  
284 study will self-identify themselves as female and black or AA. This study population was  
285 chosen as AA women are disproportionately impacted by physical inactivity and asthma  
286 compared to Caucasian men and women and AA men. In particular, AA women have  
287 the highest rates of asthma-related mortality and asthma-related health-care utilization.  
288 Physical inactivity in asthma is particularly relevant because it is associated with worse  
289 asthma outcomes, specifically, poor asthma control and respiratory function, greater  
290 health care utilization, and poorer quality of life. Research aimed at addressing physical  
291 inactivity and asthma control in this vulnerable population of women is needed.  
292

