613 Actigraph accelerometer: This will be given to participants to assess their baseline  
614 and post-intervention daily number of steps. Participants will be verbally instructed  
615 to wear it attached to their wrist at all times while awake. The Actigraph  
616 accelerometer (Figure 3) is a research accelerometer (1.8 inches at its largest  
617 dimension, weight 19 grams). This will be returned within 2 weeks of the data  
618 collection visit. The accelerometers can be returned either in person at the asthma  
619 and PA session, in a postage paid envelope or the participant and the research  
620 assistant will find a mutually agreeable place to pick up the accelerometer from the  
621 participant. The participant will not incur any charges if the accelerometer is lost or  
622 stolen. The data from the accelerometers will be downloaded to Actigraph software  
623 (ActiLife 6.13.3) when the accelerometers are returned. Only study ID will be used

624 in the actigraph software. No identifiable information will be maintained in the  
625 Actigraph software.

626  
627 Participants are typically asked to wear the accelerometer for 7 days (does not  
628 have to be consecutive). However, valid baseline measurement of activity can be  
629 obtained with an average of 10 hours per day for 4 days. This is the minimum  
630 amount of accelerometer data required to continue participation in the intervention.  
631 If the participant does not wear the accelerometer for sufficient time to provide valid  
632 baseline measure (ie. an average of 10 hours per day for 4 days), they will be  
633 offered a second opportunity to wear the accelerometer. If the participant declines  
634 or is unable to wear the accelerometer again within 3 weeks of returning the  
635 accelerometer, then the participant will be withdrawn from the study.

636  
637 **Enhanced Usual Care Group (home-based walking program):** The comparison  
638 group will be instructed to achieve a static goal of 10,000 steps per day. The US  
639 Surgeon General recommends accumulating 30 minutes of activity most days of the  
640 week. Assuming that an individual gets 6,000 steps from their other daily activities, 30  
641 minutes of walking can help one achieve a goal of approximately 10,000 steps per day.

642  
643 Participants will be given a Fitbit Charge HR® which will measure their daily steps (see  

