714 location that is in close approximation to where the participants live. The exact CPD  
715 location will be determined with the help of the Chicago Park District liaison and will take  
716 into account safety of the participants and the location of where participants live. The  
717 Chicago Park District will only provide space for these visits and no Chicago Park  
718 District staff are involved in the research as recruiters, interventionists, asthma  
719 educators or to collect data.

720  
721 At each group session the following will occur:

- 722 1. Women will attend a 2 hour group session at the Chicago Park District or at  
723 UI Health/UIC. At the group session, participants will continue to receive  
724 asthma education (short videos and/or didactic session), watch a video on  
725 how to get started to walk and what barriers they may face. Participants will  
726 be asked to share their experiences engaging in physical activity with asthma.
- 727 2. Participant will be given an individualized step-goal not to exceed 3000 steps  
728 above their baseline calculated from accelerometer data over the entire  
729 course of the study.
- 730 3. Each participant will be given an ACTION participant manual (1st group  
731 session only).
- 732 4. Participants will be encouraged to walk during the group session for up to 15  
733 minutes. The interventionist and Chicago Park District liaison will identify safe  
734 locations for the women to walk at the group session site. Women will be able  
735 to walk at their own pace and stop at anytime. If the participant does not want  
736 to participate in the walking portion of the group visit they may opt-out by  
737 verbally telling the interventionist that they do not want to participate.
- 738 5. Participants will be asked to complete a session evaluation form. (Appendix  
739 9).
- 740 6. Participants will be given \$5 cash to assist with travel expenses incurred for  
741 each group visit.

742

743 At the last group session in the adoptive phase, the following procedures will occur and  
744 the participant will receive \$35 cash or gift card for this visit only:

745 :

- 746 1. Spirometry performed according to American Thoracic Society guidelines.  
747 Participants will be asked to wear nose clips and to take a deep breath in and  
748 blow their breath out as fast as they can into the spirometer. We will perform  

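### Aim 3 is described as a pilot in sedentary women, but its inclusion list (4.1.b) sets no activity limit

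*Combined protocol and SAP*

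**What the plan says.** Section 3.0 states Aim 3 as: "Pilot test ACTION intervention in 80 sedentary AA women with asthma to assess acceptability, feasibility and estimate the efficacy to appropriately power" a later trial. The same section opens with "The proposed study has 5 aims involving a total of 135 sedentary AA women with" asthma. Section 4.0, whose heading covers Aims 1, 2 and 3, names sedentary women under its eligibility considerations. Section 4.3 gives the focus population as "sedentary African-American (AA) women with asthma. All participants included in the" study, after which the sentence turns to sex and race.

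The only activity threshold is in section 4.1.a, for Aims 1 and 2: self-report of less than 150 "min/week of moderate intensity PA". The Aim 3 list in 4.1.b has six items: sex and race, age, ACT below 20, consent, a smartphone or tablet, and "Willing to be randomly assigned to treatment or control group". None refers to activity.

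The step goals in section 6.0 (Aim 3) also bear on the point. The comparison "group will be instructed to achieve a static goal of 10,000 steps per day". The stated reasoning begins "Assuming that an individual gets 6,000 steps from their other daily activities, 30" and goes on to say that this many minutes of walking brings the total to about 10,000. In the intervention arm, "Participant will be given an individualized step-goal not to exceed 3000 steps" above her own accelerometer baseline.

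**The concern.** The population statements and the operative criteria disagree about who may enter the randomized pilot. Staff who follow 4.1.b would enrol active women; a reader of the aims would assume that none were enrolled.

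Two things are at stake. First, Aim 3 is meant to supply the effect size for the next trial. If that trial is planned in sedentary women, an estimate from a mixed sample may not carry over. Second, the contrast between the arms depends on baseline activity, because one arm has a fixed target and the other a target relative to baseline. Admitting active women therefore changes what is being compared, as well as the description of the sample.

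**Working it through.** **1. Are the 80 pilot women counted as sedentary?** Section 3.0 gives Aim 1 = 30, Aim 2 = up to 10, Aim 3 = 80 and Aims 4/5 = up to 15. The sum is 30 + 10 + 80 + 15 = 135, which reproduces the stated total of sedentary women. All 80 are included in it.

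**2. Does any other provision limit activity in Aim 3?**

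| Provision | Activity limit? |
|---|---|
| 4.1.a, Aims 1 and 2 (5 items) | Yes, 1 item: below 150 min/week |
| 4.1.b, Aim 3 (6 items) | None |
| 4.2.b, Aim 3 exclusions (11 items) | None; investigator discretion is confined to safety or adherence |
| EASY questionnaire (4.2.b) | None; it screens for health conditions |
| Baseline accelerometer rule (6.0) | None; it sets wear time only (10 hours/day for 4 days) |
| Section 11.0, Aim 3 | None; selection is by asthma severity, age and BMI |

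**3. Could an item have been lost from 4.1.b in text extraction?** In the extracted text the list under 4.1.c is missing, so this needs checking. List 4.1.a carries 7 printed line numbers (194 to 200): 5 items, one of which wraps, make 6 lines, plus a blank. List 4.1.b carries 8 (202 to 209): 6 items make 7 lines if the ACT item (82 characters) wraps, plus a blank. In the similar bulleted list of 4.2.b, a 78-character item fits on one line, while the COPD item breaks where one more word would have made 79. The ACT item therefore very likely wraps, and the count fits a complete list.

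**4. How does the contrast depend on baseline activity?** By the protocol's own conversion, 10,000 − 6,000 = 4,000 steps per 30 minutes. Assume the activity is walking. Average steps per day are then 6,000 + 4,000 × (weekly minutes / 30) / 7.

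| Walking, min/week | Average steps/day | Increase asked, control | Increase asked, intervention |
|---|---|---|---|
| 0 | 6,000 | 4,000 | up to 3,000 |
| 150 | 6,000 + 4,000 × 5/7 = 8,857 | 10,000 − 8,857 = 1,143 | up to 3,000 |
| 210 | 6,000 + 4,000 × 7/7 = 10,000 | 0 | up to 3,000 |

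The arm that asks for the larger increase can switch between the first and second rows. These are goals, not achieved steps.

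**5. What could this do to the estimate?** Let p be the share of active women and r the effect in active women divided by that in sedentary women. Relative to the sedentary effect, the mixed effect is 1 − p(1 − r). With unchanged SD, the next trial's required size scales as 1/(mixed effect)². The documents give neither p nor r, so both are assumed. The upper value for p is a loose ceiling from section 2.0, where fewer than 25% of AA women with asthma are said to be regularly active; that is a broader population, and regular activity is not defined.

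| p | r | Mixed effect | Sample-size ratio |
|---|---|---|---|
| 0.10 | 0 | 0.90 | 1.23 |
| 0.10 | 0.5 | 0.95 | 1.11 |
| 0.10 | 1.5 | 1.05 | 0.91 |
| 0.25 | 0 | 0.75 | 1.78 |
| 0.25 | 0.5 | 0.875 | 1.31 |
| 0.25 | 1.5 | 1.125 | 0.79 |

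At r = 1 both ratios are 1 for any p.

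**The case against.** The strongest reply is that the text cannot settle the matter. The 4.1.c list did not survive extraction. The wrapping argument is not decisive either: some bulleted lines elsewhere, with possibly different indents, hold 81 to 86 characters. If the ACT item fits on one line, one line number is left over, enough for a missing activity item. The pilot's own screening form and script are named among the recruitment documents but not reproduced, and may ask about activity. This uncertainty stands, and the PDF page and the form should be checked. A question on a screening form would still leave the protocol's criteria at odds with its stated population.

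The 135 total can also be called a loose label. Its sentence counts five aims where six are listed, and it includes the Aim 4/5 women, who are not called sedentary where they are described. That is fair, but Aim 3 itself uses the word, so the point does not depend on the total.

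Finally, harm is not demonstrated. The range in step 5 straddles 1, its inputs are assumptions, and step 4 concerns step goals rather than asthma control. Aim 3 is a pilot with no sample size calculation. All of this is true, and it limits the claim to an inconsistency with unknown consequences.

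**Conclusion.** The concern holds. In the extracted protocol, Aim 3 is defined in sedentary women, while its criteria admit women at or above 150 min/week. Confidence is medium because a lost list item cannot be fully excluded. The documents do not show whether the omission was deliberate. They also never formally define sedentary; 150 min/week is the only measurable version they offer.

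Randomization protects the comparison between arms. What is affected is the population to which the efficacy estimate applies and the contrast that it measures. Under the stated assumptions (10% to 25% active, effect ratio 0 to 1.5), the next trial could need anywhere from 1.78 to 0.79 times the sample size planned from the mixed estimate; the real figure depends on who enrols. This should be fixed, but it does not invalidate the pilot.

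A separate, minor conflict is that the section 4.0 narrative gives sub-optimal control as ACT of 20 or more, whereas lists 4.1.a and 4.1.b both use ACT below 20.

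**What to change.** First check 4.1.b against the PDF and the pilot screening form. If the item is absent, do one of the following:

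- Add the 4.1.a activity criterion to 4.1.b. This costs one line and a screening question already used in Aims 1 and 2; it narrows the eligible pool somewhat.
- If the omission was deliberate, remove the word sedentary from the Aim 3 population statements in 3.0, 4.0 and 4.3, and give the reason. This costs a wording edit.

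If women are already enrolled, report how many in each arm were at or above 150 min/week at baseline. Give the efficacy estimate in those below it as a supplementary analysis, provided the baseline activity questionnaires allow minutes per week to be derived. A subset of fewer than 80 women will give a less precise estimate.

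If minutes cannot be derived, report baseline accelerometer steps per day by arm. This is a weaker fallback. Steps do not classify women against a threshold in minutes. Randomization is listed at Visit 1, before the accelerometer is worn, and women without valid wear are withdrawn, so some randomized women would be missing.

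Separately, reconcile the ACT statement in 4.0 with the two lists.

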**4.2.b. Aim 3**

- 230 • Plans to relocate outside of the Chicagoland area during the study period.
- 231 • Unable to ambulate without human assistance (ie. use of a wheelchair, scooter)
- 232 • History of significant mental illness (e.g. uncontrolled bipolar disorder,
- 233 psychoses)
- 234 • Currently pregnant, planning to become pregnant over the next 3 months
- 235 • Diagnosis of COPD (emphysema or chronic bronchitis) suggested by patient
- 236 report of doctor diagnosis or smoking history (>20 pack years)
- 237 • Poorly controlled high blood pressure (BP >180/100 at baseline visit)
- 238 • Family/household member of another study participant or staff member
- 239 • Inability to speak, read or understand English;
- 240 • Investigator discretion for safety or protocol adherence reasons
- 241 • Participation in Aim 2 of this study

242

243 We will use the Exercise Assessment and Screening for You (EASY) questionnaire  
 244 (Appendix 3 to detect the presence of conditions that could preclude study participation.  
 245 Current physical activity (PA) screening guidelines from a consensus group from the  
 246 American Heart Association and the American College of Cardiology no longer  
 247 recommend routine stress testing for those initiating a PA program. The EASY  
 248 questionnaire has clear recommendations for when evaluation by a physician is needed  
 249 before beginning a PA program (e.g., when the individual reports new-onset shortness  
 250 of breath, pain, or dizziness that has not been previously evaluated by a health care  
 251 provider), and we will follow these recommendations.

252

253 If the EASY questionnaire recommends that a potential participant be evaluated by a  
 254 health care provider prior to starting a PA program, the potential participant will be  
 255 asked to contact their health care provider or we will obtain permission from the  
 256 participant to contact their UI Health provider. We will send their UI Health provider a  
 257 secure message describing the study and it's procedures and the results of their  
 258 patient's EASY questionnaire. We will request a response regarding permission of entry  
 259 into the study. Permission from their health care provider will be required prior to  
 260 participation in any study activities.

261

262 **Exclusion criteria for spirometry procedure only done at 1 data collection visit**  
 263 **(Visit 1) in the pre-pilot and 3 data collection visits in the pilot: chest or abdominal**  
 264 **surgery in previous 6 weeks, detached retina or eye surgery in previous month.**

265 **NOTE: This will be assessed at data collection visits only. If participant meets**  
266 **these exclusion criteria, then spirometry will not be performed.**  
267

